## 8.3 Assessments of Adverse Events

Each adverse event will be assessed for severity, causality, seriousness and expectedness as described below.

### 8.3.1 Severity

Category	Definition
Mild	The adverse event does not interfere with the participant's daily routine, and does not require intervention; it causes slight discomfort
Moderate	The adverse event interferes with some aspects of the participant's routine, or requires intervention, but is not damaging to health; it causes moderate discomfort
Severe	The adverse event results in alteration, discomfort or disability which is clearly damaging to health

### 8.3.2 Causality

The assessment of relationship of adverse events to the administration of IMP is a clinical decision based on all available information at the time of the completion of the case report form.

The following categories will be used to define the causality of the adverse event:

Category	Definition

Related	A causal relationship between an IMP/investigational treatment and an adverse event is at least a reasonable possibility, i.e., the relationship cannot be ruled out.
Not related	There is no reasonable possibility of a causal relationship between an IMP/investigational treatment and an adverse event.

### 8.3.3 Expectedness

Category	Definition
Expected	An adverse event which is consistent with the information about the IMP listed in the current approved Reference Safety Information (RSI) for the trial.
Unexpected	An adverse event which is not consistent with the information about the IMP listed in the current approved Reference Safety Information (RSI) for the trial.

The RSI for this trial is the Investigator Brochure for Recombinant tissue plasminogen activator (rtPA) – alteplase. As the IMP rtPA (Actilyse) is being used outside its authorised indication and route of administration all SARs will be assessed as unexpected and classified as SUSARs, and will be subject to expedited reporting to the MHRA and REC.

### 8.3.4 Seriousness

All events are assessed for seriousness as defined for an SAE in section 8.1.

All SAEs and reported in line with the procedures set-out in section 8.4 apart from regulatory reporting.

## 8.4 Procedures for recording and reporting Serious Adverse Reactions

All SAEs will be recorded in the medical records in the first instance. Only serious adverse events assessed as likely to be related to IMP administration, Serious Adverse Reactions (SARs), will be recorded in the CRF, and the sponsor's SAE log. The SAE log will be reported to the sponsor at the end of the study.

SARs will be recorded from the start of treatment until the end of the study.

All SARs must be recorded on a SAE Reporting Form. The CI/PI or designated individual will complete the sponsor's SAE form and email to the Sponsor at [contact] immediately and no later than 24 hours of his / her becoming aware of the event. The Chief or Principal Investigator will respond to any SAE queries raised by the sponsor as soon as possible.

Completed SAE forms must be sent within 24 hours of becoming aware of the event to the Sponsor

Email forms to [contact]

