## 8.1 Definitions

Term	Definition
Adverse Event (AE)	
Any untoward medical occurrence in a patient or clinical trial participant administered a medicinal product and which does not necessarily have a causal relationship with this treatment. Therefore an AE can be any unfavourable or unintended change in the structure (signs), function (symptoms) or chemistry (laboratory data) in a participant to whom an IMP or procedural intervention has been administered, including occurrences which are not necessarily caused by or related to that product.

Adverse Reaction (AR)	
Any untoward and unintended response in a participant to an investigational medicinal product which is related to any dose administered to that participant.
 
This includes medication errors, uses outside of protocol (including misuse and abuse of product)

Serious Adverse Event (SAE), Serious Adverse Reaction (SAR) or Unexpected Serious Adverse Reaction	
Any adverse event, adverse reaction or unexpected adverse reaction, respectively, that:
 
 
• results in death,
 
• is life-threatening*,
 
• requires hospitalisation or prolongation of existing hospitalisation**,
 
• results in persistent or significant disability or incapacity, or
 
• consists of a congenital anomaly or birth defect
 
 
*A life-threatening event, this refers to an event in which the participant was at risk of death at the time of the event; it does not refer to an event which hypothetically might have caused death if it were more severe.
 
** Hospitalisation is defined as an in-patient admission, regardless of length of stay. Hospitalisation for pre-existing conditions, including elective procedures do not constitute an SAE.
 
Some medical events may jeopardise the subject or may require an intervention to prevent one of the above characteristics/consequences. Such important medical events should also be considered as serious.
 
The term “severe” is often used to describe the intensity of an event or reaction (e.g. mild, moderate or severe) and should not be confused or interchanged with the term “serious”.

Suspected Unexpected Serious Adverse Reaction (SUSAR)	A serious adverse reaction, the nature, severity or outcome of which is not consistent with the Reference Safety Information.

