## 8.2 Recording adverse events

All adverse events will be recorded in the medical records in the first instance. Non-serious AEs will not be collected in the CRFs for this trial, apart from the adverse events of special interest (AESI) listed below:

- Bleeding events

In addition, any Serious Adverse Events (SAEs) assessed as likely to be related to IMP administration will be collected. See section 8.4 for further details on recording and reporting of Serious Adverse Reactions (SARs). These AESIs and Serious Adverse Reactions (SARs) will be recorded with clinical symptoms and accompanied with a simple, brief description of the event, including dates as appropriate, until the participant completes the trial.

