## 8.5 Notification of deaths

Only deaths assessed as likely related to IMP administration will be reported to Sponsor, see section 9.4 above.

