### 10.1.2 Safety

1. Incidence and severity of major bleeding events directly attributable to the study drug
2. Decrease in fibrinogen levels to  $< 1.0 \text{ gm/L}$  during treatment period and 48 hrs after the last dose of treatment
3. Number and nature of serious adverse events causally related to the treatment

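### Protocol sections 8.2, 8.4 and 8.5 act on serious events only when 'likely' related, a stricter test than the causality rule in 8.3.2, so a related non-bleeding SAE can miss the CRF, the third primary safety endpoint and SUSAR reporting

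*Protocol*

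**What the plan says.** Protocol section 8.3.2 has only two causality categories. An event is related when a causal link "is at least a reasonable possibility, i.e., the relationship cannot be ruled out"; otherwise it is not related. There is no 'likely' grade. Section 8.1 fits this: an adverse reaction is "Any untoward and unintended response in a participant to an investigational medicinal product which is" related to any dose given.

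Three later sections use another word:

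- Section 8.2, on what is collected beyond bleeding events: "any Serious Adverse Events (SAEs) assessed as likely to be related to IMP administration will be collected".
- Section 8.4, on the CRF and the sponsor's SAE log: "Only serious adverse events assessed as likely to be related to IMP administration, Serious Adverse Reactions (SARs), will be recorded in the CRF".
- Section 8.5, on deaths: "Only deaths assessed as likely related to IMP administration will be reported to Sponsor, see section 9.4 above".

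Section 8.3.4 gives a further rule: SAEs in general follow the 8.4 procedures, regulatory reporting excepted.

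The third primary safety endpoint in section 10.1.2 is "Number and nature of serious adverse events causally related to the treatment". Section 8.3.3 classifies every serious adverse reaction in this trial as a SUSAR.

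**The concern.** 'Likely' is a higher bar than a link that cannot be excluded. An SAE between the two bars is related by the protocol's own definition, yet the collection rules do not admit it.

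Three things depend on those rules. The third primary safety endpoint can count only what reaches the CRF. Expedited reporting is tied to reaction status under 8.3.3, and the 7- and 15-day limits in 8.6 run from when the sponsor learns of the event, so an event stopped at 8.4 starts no clock. The TMG (section 12.1) and SAP 6.3 both refer to SAEs, while the CRF and SAE log would hold only the 'likely' ones.

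The middle ground matters in this trial. The risk table in section 2.6 lists hypersensitivity (including bronchospasm and shock) and anaphylaxis, with frequency unknown by this route, and section 5.2 says the irritant effect on the lungs is not known. In patients with ARDS such events may be hard to tell from the disease. Cohort 2 also drops the exclusion for taking part in another drug trial and has no control group, which makes attribution harder.

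**Working it through.** The plan states no figure on this point, so the check is a comparison of text, followed by one illustration.

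**Step 1: set the rules side by side.**

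| Protocol section | What it governs | Test for relatedness |
|---|---|---|
| 8.1 | Definition of adverse reaction | Related |
| 8.3.2 | Causality category | Cannot be ruled out |
| 8.2 | SAEs collected | Likely |
| 8.4 | SAEs in CRF and SAE log | Likely |
| 8.5 | Deaths notified to sponsor | Likely |
| 8.3.4 | SAEs sent through 8.4 | None (all SAEs) |
| 10.1.2 | Primary safety endpoint 3 | Causally related, not tied to any definition |

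This gives three thresholds for one decision: cannot be ruled out, likely, and no threshold.

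**Step 2: follow one event.** Take a non-bleeding SAE that the investigator thinks possibly, but not probably, due to rtPA.

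1. Under 8.3.2 it is related, because the link cannot be excluded.
2. Under 8.1 it is a serious adverse reaction, and under 8.3.3 a SUSAR.
3. Under 8.2 and 8.4 as worded, it is not likely related, so it goes into the medical records but not the CRF or SAE log.
4. It is then absent from endpoint 3, and the 8.4 route to the sponsor does not carry it.
5. Section 15 plans no prospective monitoring, so no scheduled check would bring it from the notes into the database.

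**Step 3: check other routes for each type of event.**

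- Bleeding events: section 8.2 collects them in the CRF as adverse events of special interest, whatever the causality. The bleeding stopping rules in 7.10 use a time window (start of treatment to 30 hours after the last dose), not a causality judgement.
- Deaths: section 7.5.1 collects death and its cause as end-of-study data, the 7.7.4 scale has death as point 7, and section 10.2 counts in-hospital mortality. None of these has a relatedness filter. Only notification to the sponsor under 8.5 is filtered.
- Other SAEs: the medical records only, unless judged likely related.

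The exposed group is therefore non-bleeding SAEs that are possibly but not likely related, plus sponsor notification of deaths of that kind.

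**Step 4: check the cross-reference in 8.5.** It points to section 9.4 as lying above. Section 9.4 covers data handling and comes later; 8.4 appears to be meant.

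**Step 5: illustration only.** Let s be the share of related SAEs that reach the CRF. The documents give neither s nor the true rate; both are assumptions here. If no related SAE is recorded among the n = 30 patients of cohort 2, the one-sided 95% upper bound on the recorded rate is 1 − 0.05^(1/30) = 9.5%. Dividing by s gives the bound on the true rate:

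- s = 1: 9.5%
- s = 0.75: 12.7%
- s = 0.5: 19.0%
- s = 0.25: 38.0%

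With an assumed true rate p of 10%, the chance that at least one is recorded is 1 − (1 − p·s)^30: 95.8% at s = 1, 78.5% at s = 0.5 and 53.2% at s = 0.25. This shows how incomplete capture would weaken a clean safety result. It does not estimate what will happen.

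**The case against.** The best defence is that nothing is meant by 'likely'. Section 8.4 places the phrase next to serious adverse reactions as if they were the same thing, 8.1 defines a reaction simply as related, and 8.4 goes on to require an SAE form for every such reaction. An investigator with only two boxes would tick related for a possible event, and it would then be reported. This reading is plausible and may be what the authors intended. But no sentence says so, the word recurs in three operative sections, and the reading leaves 8.3.4 in conflict with 8.4.

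A second defence is that much is captured regardless of cause: bleeding, the main foreseen risk, along with deaths and the medical records. This stands and narrows the point.

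It also rules out stronger claims. A reader might infer that deaths are captured only when likely related; sections 7.5.1 and 10.2 show that they are not filtered in this way. A reader might also infer that some definite number of cohort 2 patients will have events lost, or that most drug-related events in such ill patients are possible rather than likely. The documents give no basis for either.

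Finally, SAP 5.1 already limits the endpoint to causally related SAEs, so the mismatch in SAP 6.3 is minor. That SAP is also written to protocol version 7.0, so editing it would not reach cohort 2.

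**Conclusion.** The protocol is wrong as written. Its definition of related and its rules for acting on related serious events use different thresholds, and 8.3.4 adds another. Taken literally, a non-bleeding SAE that is possibly but not likely related can be missing from the CRF, the SAE log, primary safety endpoint 3 and expedited reporting. For deaths, the gap is confined to sponsor notification.

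The contradiction can be read directly from the text and needs no assumption. Its consequence rests on one: that site staff apply 'likely' in its ordinary sense, as more than a link that cannot be excluded. If they treat the two as the same, no event is lost and the correction only adds clarity. How many events are affected cannot be estimated from the documents.

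**What to change.** 1. In protocol 8.2, 8.4 and 8.5, replace the 'likely' wording with: related as defined in section 8.3.2. Use the same term for the third safety endpoint in 10.1.2 and in the Summary.
2. Reconcile 8.3.4 with 8.4, so that it is clear whether all SAEs or only related ones follow the 8.4 procedure.
3. Correct the reference to section 9.4 in 8.5; 8.4 appears to be meant.
4. In SAP 6.3, limit the SAE summary to causally related events, to match SAP 5.1, and carry the 8.3.2 definition into the separate cohort 2 SAP promised in protocol 10.6.

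The cost is a wording amendment and possibly a few more SAE forms. No new assessment or visit is needed, since all SAEs are already in the medical records.

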## 8.5 Notification of deaths

Only deaths assessed as likely related to IMP administration will be reported to Sponsor, see section 9.4 above.

## **8.6 Reporting of SUSARS**

The sponsor will notify the main REC and MHRA of all SUSARs. SUSARs that are fatal or life-threatening must be notified to the MHRA and REC within 7 days after the sponsor has learned of them. Other SUSARs must be reported to the REC and MHRA within 15 days after the sponsor has learned of them.

## **8.7 Development Safety Update Reports**

The sponsor will provide the main REC and the MHRA with Development Safety Update Reports (DSUR) which will be written in conjunction with the trial team and the Sponsor's office. The report will be submitted within 60 days of the Developmental International Birth Date (DIBD) of the trial each year until the trial is declared ended.

## **8.8 Pregnancy**

Not applicable. All female patients of child bearing potential must have a confirmed negative pregnancy test prior to enrolment (within 24hrs) and will remain in-patients in hospital during the course of the study.

## **8.9 Reporting Urgent Safety Measures and other safety events**

If any urgent safety measures are taken the CI/ PI shall immediately and in any event no later than 3 days from the date the measures are taken, give written notice to the MHRA, the relevant REC and Sponsor of the measures taken and the circumstances giving rise to those measures.

## **8.10 Notification of Serious Breaches to GCP and/or the protocol (SPON/S15)**

A "serious breach" is a breach which is likely to effect to a significant degree –

- (a) the safety or physical or mental integrity of the participants of the trial; or
- (b) the scientific value of the trial.

The sponsor of a clinical trial shall notify the licensing authority in writing of any serious breach of –

- (a) the conditions and principles of GCP in connection with that trial; or (b) the protocol relating to that trial, as amended from time to time, within 7 days of becoming aware of that breach.

The sponsor will be notified immediately of any case where the above definition applies during the trial conduct phase. The sponsor's SOP on the 'Notification of violations, urgent safety measures and serious breaches' will be followed.

# **9 Data management and quality assurance**

## **9.1 Confidentiality**

All data will be handled in accordance with the UK Data Protection Act 2018.

The Case Report Forms (CRFs) will not bear the participant's name or other personal identifiable data. The participant's initials, date of birth and trial identification number, will be used for identification and this will be clearly explained to the patient in the Patient information sheet. Patient consent for this will be sought.

## 9.2 Data collection tools and source document identification

Data will be collected on Trial specific case report forms (CRFs).

Source data are contained in source documents (medical notes and laboratory reports) and must be accurately transcribed on to the CRF.

It is the responsibility of the investigator to ensure the accuracy of all data entered in the CRFs. The delegation log will identify all those personnel with responsibilities for data collection and handling, including those who have access to the trial database.

## 9.3 Completing Case Report Forms

All CRFs must be completed and signed by staff that are listed on the site staff delegation log and authorised by the CI/ PI to perform this duty. The CI/ PI is responsible for the accuracy of all data reported in the CRF. Once completed the original will be kept with the study team at site.

## 9.4 Data handling and analysis

A trial specific data management SOP will be in place for the trial. This will contain details of the software to be used for the database, the process of database design, data entry, data quality checks, data queries, data security, database lock.

Where data are transferred electronically this will be in accordance with the UK Data Protection Act 2018 as well as UCL Information Security Policy and Trust Information Governance Policy. There will be a documented record of data transfer and measures in place for the recovery of original information after transfer.

# 10 Statistical Considerations

## 10.1 Primary endpoints

### 10.1.1 Efficacy

1. Change in  $\text{PaO}_2/\text{FiO}_2$  ratio from baseline (as defined in sections 7.1.2 and 7.1.3), daily during treatment, end of treatment, 3 days post end of treatment and 5 days post end of treatment.

### 10.1.2 Safety

1. Incidence and severity of major bleeding events directly attributable to the study drug
2. Decrease in fibrinogen levels to  $< 1.0 \text{ gm/L}$  during treatment period and 48 hrs after the last dose of treatment
3. Number and nature of serious adverse events causally related to the treatment

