## 2.5 Dosing schedule of rtPA for cohort 2 – rationale

During the first surge 9 patients were recruited to the pilot study, with 6 patients receiving IMV and 3 patients receiving non-invasive oxygen support. When the first surge died out, recruitment was not feasible and following discussion with DMC and TMG cohort 1 was closed for further recruitment and historical controls were recruited for evaluation of efficacy to enable a sample size calculation for a larger phase 3 study.

None of the bleeding events were considered related to the tPA. See preliminary safety data for cohort 1 in section 2.7. Final analysis of data is awaited; preliminary review of data is described here.

Preliminary data from the 9 patients from cohort 1 indicated a potential increase in arterial oxygen saturation levels, and importantly no evidence of consumption of fibrinogen nor a decrease in plasminogen levels was observed unlike the changes associated with intravenous administration.

Protocol v8.0 has been prepared at the start of the second UK surge. 30 patients will be recruited to this second cohort, with a minimum recruitment of 10 IMV patients and minimum of 10 patients receiving non-invasive ventilation. Early initiation of treatment appears to more effective, and this may be related either to lower fibrin burden or higher amount of plasminogen from the plasma exudate the substrate for rtPA. In the NIV and standard oxygen therapy group, a loading dose of 20 mg three times a day for 2 days followed by 20 mg twice a day is reasonable as intermittent fibrinolysis is effective. The loading dose potentially can help overcome the accumulation of PAI-1 early in the disease process, and is strong inhibitor of fibrinolysis.

The effect on arterial oxygen saturation levels appears to be less in IMV patients and drug losses can be expected because of the dead space created by the ventilator circuit. To account for this, we propose 20 mg every 8 hrs in patients receiving IMV.

Although the pilot study has used nebulisation every 6hrs, it is very reasonable to decrease the frequency to either twice a day for the non-invasive oxygen support group, or three times a day for the IMV group. The less frequent administration should make it easier for delivery teams.

The maximum duration of treatment will continue to be 14 days with a provision for early termination as described in section 7.3.3.

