In total, 7 bleeding events were identified. A bleed was considered not related to alteplase if the event happened 30 hrs after the last dose of treatment, alteplase exposure time period. Six of the seven bleeds were beyond alteplase exposure time period, and one was within the time period.

One bleed each met the criteria for ISTH major and minor bleed. Five bleeds did not meet the ISTH criteria for minor or major bleeds. The severity of bleeds as assessed for adverse event reporting resulted in five bleeds being categorised as mild and two events as moderate.

The severity assessment as used for AE reporting was used to further describe the bleeds.

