### **10.6.2 Primary outcome analysis**

The PaO2/FiO2 ratio measured over time will be described for each group. The change from baseline in the PaO2/FiO2 ratio will be summarised at each post baseline timepoint. Plots will be used, where appropriate, to show the PaO2/FiO2 summarised for patients over time.

PaO2/FiO2 will be a calculated field on the trial database derived from the fields for PaO2 and FiO2. For cohort 2 data will be extracted once a day coinciding with the worst PF ratio. As PF ratio is the primary endpoint, in addition to the worst PF ratio, up to a maximum of 6 data points spread across 24 hrs that represents patients clinical status will be extracted. Details of further data derivation and analyses will be described in the SAP.

All patient data will be used, regardless of any intercurrent events that may have occurred after enrolment:

- Data from patients recruited into the rtPA + SOC group will be summarised whether or not patients have received all planned doses of the IMP.
- Any change in requirement for oxygenation and ventilation support will be summarised and described
- Changes in PaO2/FiO2 ratio over time will be described and interpreted taking into consideration that a patient's condition may have changed and led to their ventilation type changed post enrolment. If data allows, additional descriptions of the PaO2/FiO2 ratio over time may be performed in each subgroup of patients experiencing such changes (e.g. IMV to NIV, or vice versa).

The incidence and severity of bleeding events will be summarised in each group, and the change in fibrinogen levels will also be summarised at each post-baseline timepoint.

For cohort 1, subject to the final sample size and data quality, outcomes will also be compared between the SOC only group and intervention (rtPA + SOC) group using appropriate regression methods to make adjustment for baseline characteristics. Appropriate data transformations required for model assumptions will be considered if necessary.

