5.1 Primary outcome measures

Efficacy

- PaO₂/FiO₂ measured at multiple timepoints over the study period: baseline, during treatment, end of treatment, 3 days post end of treatment and 5 days post end of treatment.

Safety

- Incidence and severity of major bleeding events;
- Decrease in fibrinogen levels to < 1.5 gm/L during treatment period and 48 hrs after the last dose of treatment;
- Number and nature of serious adverse events causally related to the treatment.

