6.3 Analysis of primary outcome

The primary outcome for efficacy is oxygenation, measured using the PaO₂/FiO₂ ratio over time. The distributions of the primary outcomes will be summarised, by group, over time. Change in PaO₂/FiO₂ ratio from baseline will be checked visually using means & SE plots. If necessary, appropriate transformations of the data will be performed (e.g., using the natural logarithm).

Subject to the final sample size and data quality, PaO₂/FiO₂ ratio will also be compared between the SOC group (historical controls) and rtPA group using appropriate regression modelling, controlling for baseline oxygenation ratio:

$$OXY_i = \beta_0 + \beta_1 \cdot T_i + \beta_2 \cdot OXY0_i + \varepsilon_i,$$

where the i subscript denotes the i^{th} patient and

- OXY_i = PaO₂/FiO₂ ratio (oxygenation) at the end of treatment;
- T_i = group indicator (= 1 if patient is in the rtPA group, = 0 otherwise);
- $OXY0_i$ = PaO₂/FiO₂ ratio (oxygenation) at baseline;
- $\varepsilon_i \sim N(0, \sigma^2)$ = Normally distributed error term.

The estimate of the parameter β_1 and associated 95% confidence interval shall be reported, as well as a p-value pertaining to the hypothesis test of

$$H_0: \beta_1 = 0 \text{ versus } H_1: \beta_1 \neq 0.$$

Similarly, the use of models using oxygenation at other meaningful timepoints as outcome measure will be evaluated. Owing to a limited sample size, models shall not adjust for other baseline characteristics. Fitted models shall be checked, where appropriate, to ensure that modelling assumptions have been satisfied. Appropriate transformations of outcomes or other suitable approaches (e.g., robust or non-parametric methods) shall be explored if model assumptions are not satisfied.

For treatment safety, the incidence and severity (either major or minor) of bleeding events will be summarised with frequencies and percentages in each group. Fibrinogen levels will also be summarised graphically using plots of the mean, by group, over time. Finally, the number and nature of serious adverse events (SAEs) will be summarised. These events are defined in section 8 of the protocol.

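### The primary bleeding endpoint is defined both with and without a drug-attribution filter, and the preliminary cohort 1 result is 0/9 or 1/9 depending on which is used

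*Protocol*

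**What the plan says.** Three places restrict the endpoint to bleeds caused by the drug. Protocol 10.1.2 lists "Incidence and severity of major bleeding events directly attributable to the study drug", and the same condition appears in the primary endpoints of Protocol section 1 and in the primary outcomes of SAP section 1.

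Three places do not. SAP 5.1 lists "Incidence and severity of major bleeding events" and stops there. SAP 6.3 plans that "the incidence and severity (either major or minor) of bleeding events will be summarised with frequencies and percentages in each group". Protocol 10.6.2 plans that "The incidence and severity of bleeding events will be summarised in each group".

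On cohort 1, Protocol 2.5 states that "During the first surge 9 patients were recruited to the pilot study". Protocol 2.7 reports seven bleeds in the treated patients, labelled preliminary, and says of their classification: "One bleed each met the criteria for ISTH major and minor bleed". It gives the attribution rule: "A bleed was considered not related to alteplase if the event happened 30 hrs after the last dose of treatment". Six of the seven fell outside that window and one fell inside. Protocol 2.5 concludes: "None of the bleeding events were considered related to the tPA".

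Protocol 8.3.2 has two causality categories, related and not related. An event is related if a causal link cannot be ruled out.

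**The concern.** A primary endpoint should yield one number from one set of data. Here a reader who follows Protocol 10.1.2 and a reader who follows SAP 5.1 would report different primary safety results from the same patients. Amendment lag does not explain the conflict inside the SAP, because its section 1 and section 5.1 belong to the same version 1.0.

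The filtered version is also the less well defined of the two. Its condition of direct attribution is not a category in Protocol 8.3.2, where the threshold for related is low. What was applied in cohort 1 was a fixed 30-hour cut-off, with a causality judgement for anything inside it, in an open-label trial. Cohort 2, which Protocol 4.1 says is meant to add safety data, has no control group against which to check such a judgement.

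At stake is the headline bleeding figure of a pilot that is meant to inform a decision on a randomised trial.

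**Working it through.** **Inputs**

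- Treated patients in cohort 1: 9, of whom 6 on IMV and 3 on non-invasive support (Protocol 2.5).
- Bleeds: 7. One was ISTH major, one ISTH minor and five neither (Protocol 2.7).
- Bleeds judged related to the drug: 0 (Protocol 2.5).

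**Consistency of the plan's own counts**

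- Patients: 6 + 3 = 9.
- Bleeds by ISTH class: 1 + 1 + 5 = 7.
- Bleeds by exposure window: 6 outside + 1 inside = 7.
- Bleeds by adverse event severity: 5 mild + 2 moderate = 7.

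The counts agree on every breakdown.

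**The endpoint under each wording**

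One major bleed can involve only one patient, so event and patient counts coincide here. The intervals are Clopper-Pearson: the lower limit L solves P(X ≥ x | L) = 0.025 and the upper limit U solves P(X ≤ x | U) = 0.025, with n = 9.

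- *Filtered (Protocol 10.1.2, SAP section 1).* x = 0. (1 − U)^9 = 0.025, so U = 1 − 0.025^(1/9) = 0.336. Result: 0/9 = 0%, 95% CI 0 to 33.6%.
- *Unfiltered (SAP 5.1).* x = 1. 1 − (1 − L)^9 = 0.025, so L = 1 − 0.975^(1/9) = 0.0028. (1 − U)^9 + 9U(1 − U)^8 = 0.025, so U = 0.482. Result: 1/9 = 11.1%, 95% CI 0.3 to 48.2%.

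**What the filter removed**

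The 30-hour rule alone removed six of the seven bleeds. The seventh was inside the window and was also judged unrelated. The available text of Protocol 2.7 does not say which of the seven was the major bleed, so there are two possibilities:

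- If the major bleed was outside the window, the fixed cut-off alone makes the filtered count zero.
- If it was inside, the causality judgement makes it zero, and a 30-hour line without that judgement would read 1/9.

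**The case against.** The strongest reply is that little is hidden. Both analysis sections already summarise bleeding without an attribution filter, all bleeds are collected as events of special interest (Protocol 8.2), and Protocol 2.7 discloses all seven. SAP 5.1 may simply be shorthand, since SAP 5.2 sends readers to the Protocol for details of the outcomes. The study is declared descriptive. This stands as a limit on the harm, but it does not settle which number is the primary endpoint. In a descriptive study that definition is the result.

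It is also fair to say that the filter is not wholly a matter of opinion, since most of the cohort 1 exclusions followed a fixed time rule. Judgement may not have touched the major bleed at all.

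Four stronger readings are tempting and are not supported:

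- *That the DMC judges safety on the attributed count.* Protocol 4.1, and 12.2 for cohort 1, give it weekly reports of major and minor bleeding. The bleeding criteria in Protocol 7.10, which trigger ad hoc review, use a time window and not causality.
- *That dropping the filter makes bleeding comparable with the historical controls.* Controls cannot have a drug-attributed bleed, so the filtered count is zero for them by construction. But the control data list in Protocol 7.5.2 does not name bleeding events, so rewording alone would not supply the comparison.
- *That the 30-hour bleeding window contradicts the 48-hour fibrinogen window.* One concerns clinical events and the other a laboratory value, and they may differ.
- *That the drug carries a higher bleeding risk than reported.* With nine patients the two intervals overlap widely, and they describe the same patients.

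**Conclusion.** The point holds as an inconsistency in the definition of a primary endpoint. It is not simply Protocol against SAP: SAP section 1 sides with the Protocol's endpoint lists, while SAP 5.1, SAP 6.3 and Protocol 10.6.2 do not filter. On the cohort 1 data the choice moves the reported result between 0/9 and 1/9.

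Those fractions rest on two assumptions: that the preliminary counts survive to the final analysis, and that the statement that no bleed was related covers the major bleed, as its wording implies.

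The unfiltered count is the better primary endpoint because it does not depend on an open-label causality call and uses events already being collected. The change should be made before the separate cohort 2 SAP promised in Protocol 10.6 is finalised.

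**What to change.** 1. Use one wording in Protocol section 1, Protocol 10.1.2, SAP section 1, SAP 5.1 and the cohort 2 SAP: all ISTH major bleeding events in treated patients, whatever the attribution.
2. State the counting window. First dose to the end of the patient's trial participation would match the collection period in Protocol 8.2. SAP 5.1 gives no window for bleeding, so this is an addition.
3. Under the primary line, show two labelled subsets: bleeds up to 30 hours after the last dose, and bleeds the investigator judged related. State the attribution rule in the terms of Protocol 8.3.2.
4. Report incidence by patient with exact 95% confidence intervals.
5. For cohort 1, whose counts are known, report both versions and state that the wording was settled after the preliminary data were seen.

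The cost is some wording and one table, with no new data on treated patients. The downside is that the stated bleeding rate becomes slightly less favourable.
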